9 RESPONSE CRITERIA

9.1 Primary Variable Assessments

The primary assessment of this study is to determine the effect of premaxillary injection on nasal tip projection and upper lip projection for perioral rejuvenation. Efficacy of the injection on the subjects' 1-month post OCR with *Restylane® Defyne* will be done through comparative measurements taken on pre and post-treatment photographs.

Nasal tip projection will be assessed by Goode's ratio. The value is defined as nasal height over the nasal length. The nasal height is measured from the alar-facial groove to the tip-defining point and the nasal length is measured from the root of the nose, or nasion, to the tip-defining point. Upper lip projection will be measured by a method outlined by Merrifield in 1966. As described, a profile line is drawn tangent to the soft tissue chin and to the most anterior point of the upper lip. This line is then extended upward to the Frankfort horizontal plane. The angle at which these two lines intersect is called the Z angle. A change in the angle to a more acute value on postoperative photographs would indicate an increase in upper lip projection. This method was chosen because it is calculated independent of any postoperative nasal changes.

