5 STUDY DESIGN

This is an open-label, prospective, postmarket study to assess the effect of premaxillary hyaluronic acid filler injection on nasal tip projection and upper lip position.

The study will enroll and treat a total of 20 subjects who are filler naïve and do not have any history of rhinoplasty, recent, 6 months upper lip augmentation, lip lift or other surgical procedures involving the upper lip, chin augmentation and orthognathic surgery. Patients in study are restricted from perioral neurotoxin or ablative resurfacing, facial cosmetic surgery, all subdermal directed aesthetic treatments or filler treatment other than which is dictated in the protocol during the course of the study.

Subjects, who fulfill all eligibility criteria, will undergo pre-treatment standardized 2D portrait photography. From the profile image, baseline nasal projection measurements will be documented according to Goode's ratio. Additionally, baseline upper lip position will be recorded by measuring the Z-angle, which is the intersection of the Frankfort horizontal line and the profile line as described by Merrifield. From the straight portrait image, the ratio of the upper lip vermilion height to the lower lip vermilion height will be documented. Subjects will then be injected with a maximum of 4 syringes of Restylane® Defyne to treat their premaxillary space per the discretion of the Principal Investigator (PI). If optimal correction result (OCR) has not been achieved additional touch-up injections of Restylane® Defyne may be injected 2 weeks post treatment visit to achieve OCR as per PI discretion.

Post OCR visits will be performed at 4 weeks following premaxillary injections. Subjects will be followed to assess any treatment-related adverse events (such as pain, nodules, swelling, redness, bruising, tenderness, itching, and headache) as well as pigmentation changes and/or keloid formation. Each subject will then be photographed with standardized photographs in a similar fashion as pre-treatment and the same measurements will be recorded.

Upon study culmination, pre-treatment and 1-month post OCR photographs will be assessed. Each patient will be evaluated to determine if nasal tip projection was increased causing an increase in upper lip projection. Additionally, the vermilion ratios will be compared to evaluate for change in upper lip vermilion height.

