6 SUBJECT SELECTION

A total of 20 subjects.

All Subjects must comply with the following inclusion and exclusion criteria:

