6.1 Inclusion Criteria

1. Subjects Age 21 to 70.
2. Subjects who demonstrate signs of perioral aging or poor upper lip projection.

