11.3 Analysis Method

The PI's study coordinator will perform all statistical analyses. This is in an effort to avoid any potential bias that could be created by the treating physician participating in the analysis. Given that there is inherent variability even in standardized portrait photography, the decision was made to perform measurements based on facial landmarks and distance ratios. Statistical analysis will be conducted using a paired *t* test.

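### The planned patient-by-patient judgement of increased tip and lip projection makes no allowance for measurement error, so noise alone would mark roughly half of subjects as increased on each measure

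*Combined protocol and SAP*

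**What the plan says.** The study has one arm: "A total of 20 subjects" (Section 6), with photographs before treatment and at the one-month visit. Section 5, repeated in the synopsis (Section 1), sets an individual determination: "Each patient will be evaluated to determine if nasal tip projection was increased causing an increase in upper lip projection". The comparison uses two time points: "Upon study culmination, pre-treatment and 1-month post OCR photographs will be assessed".

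Section 9.1, under the response criteria, gives the direction for the Z-angle: "A change in the angle to a more acute value on postoperative photographs would indicate an increase in upper lip projection". For Goode's ratio it gives only the definition: "The value is defined as nasal height over the nasal length". The visible text states no minimum change, second reading or measurement-error limit for either measure. The Appendix B measurement diagram is not shown in the copy reviewed.

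Section 11.3 acknowledges the noise: "Given that there is inherent variability even in standardized portrait photography". Its answer is to use facial landmarks and distance ratios. The only test it names is a paired t test. Section 11.2 describes the endpoint as a comparison of photographs before and after treatment and defines no responder rate.

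**The concern.** If the only criterion is direction, each patient is compared with their own single pre-treatment reading, and any favourable difference can be called an increase. Distance ratios remove camera-scale error. They do not remove error in marking landmarks, or in pose and lip posture between visits. A directional rule lets that error through in full.

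What is at stake is any statement about individuals. The clinical hypothesis in Section 1 is that subjects gain tip projection and have an associated gain in lip projection. The per-patient determination is the only planned step that looks at both within one person. With no control arm, the data do not show how many patients would appear to gain on both if the injection did nothing. A report that 7 of 20 showed both increases would read as support, although 7 is within the range expected from noise. Whether one change causes the other is a separate question and is not raised here.

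**Working it through.** **Inputs.** From the documents: 20 subjects, one reading before and one after, favourable direction only, no minimum change. Not in the documents, so assumed: symmetric error with the same distribution at both visits, independent subjects, and an error correlation rho between the changes in the two measures, varied from -0.5 to 0.7. The plan gives no false-increase rate and no derivation of the sample size, so it has no figure of its own to reproduce.

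**One measure, no true effect.** P(favourable change) = 0.5 whatever the size of the error. Expected count 20 × 0.5 = 10; Binomial(20, 0.5) 95% range 6 to 14.

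**Rounded readings.** Ties lower the rate. Simulated rates were 46.5%, 43.0% and 36.4% for a rounding unit of 0.25, 0.5 and 1.0 times the single-reading SD. A coarser unit of twice the SD gives 25.7%.

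**Both measures, no true effect, no ties.** P(both favourable) = 1/4 + arcsin(rho)/(2π), assuming bivariate normal errors.

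| rho | P(both) | Expected of 20 |
|---|---|---|
| -0.5 | 16.7% | 3.3 |
| -0.3 | 20.2% | 4.0 |
| 0 | 25.0% | 5.0 |
| 0.3 | 29.9% | 6.0 |
| 0.5 | 33.3% | 6.7 |
| 0.7 | 37.3% | 7.5 |

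At rho = 0, Binomial(20, 0.25) has a 95% range of 2 to 9, and the chance of at least one apparent responder on both is 1 − 0.75^20 = 99.7%. Rounding lowers these figures too: at 36.4% per measure and independent errors, 0.364² = 13%.

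**Discrimination.** With a true mean shift of 0.5 SD of the change, 69.1% of subjects would move the favourable way, or 20 × 0.691 = 13.8. That is still inside the no-effect range of 6 to 14.

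**Group test.** The paired t test sets the mean change against its own variability, so it allows for this noise. At an assumed two-sided 0.05 (the plan states no level), its false-positive rate in the favourable direction is 2.5% per measure.

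**Would a limit from left-right differences repair the individual rule?** Appendix A requires both profiles, so one could take half the SD of (left change minus right change) as the error SD of the two-side mean and set a limit at 1.96 times that. Let each side's change have error SD σ, with correlation r between sides.

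- Error SD of the mean of the two sides: σ√((1+r)/2).
- Half the SD of the difference: σ√((1−r)/2).
- Effective limit in true SDs: 1.96 × √((1−r)/(1+r)).

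At r = 0 the no-effect rate is 2.5% with the SD known, and 3.3% by simulation with the SD estimated from 20 subjects. For shared error:

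- r = 0.3: limit 1.96 × 0.734 = 1.44 SD, rate 7.5%.
- r = 0.5: limit 1.96 × 0.577 = 1.13 SD, rate 13%.
- r = 0.8: limit 1.96 × 0.333 = 0.65 SD, rate 26%.

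Simulation with the SD estimated from 20 subjects gave 8%, 14% and 26%. Averaging the two sides is sound in itself: with equal side variances, the error variance is multiplied by (1+r)/2, which cannot exceed 1.

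**The case against.** The strongest reply is that the Section 9.1 sentence is a sign convention. It explains that a smaller angle means more projection, and the same sentence appears in Section 2 where the earlier rhinoplasty study is described. That stands: the sentence is not a formal responder threshold, and for Goode's ratio the rule is only inferred. What remains is that Sections 1 and 5 require a determination for each patient and supply nothing but direction to make it with.

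A second reply is that no responder count or rate is planned and the only test is on the mean. That also stands. A reader might infer that the plan has a responder endpoint, or that its formal test has an inflated error rate. The documents support neither. The t test, however, does not correct a judgement about an individual.

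A third reply is that Appendix A standardises camera position, the Frankfort plane, rotation and lip posture. This should reduce the error, but with continuous readings the no-effect rate of one half does not depend on error size.

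Two further inferences should be resisted. One is that the lack of a numerical entry cut-off ("Subjects who demonstrate signs of perioral aging or poor upper lip projection", Section 6.1) is what makes baseline the line to cross. Change is measured from baseline whatever the entry criteria are. Selection on the same reading could push the rate above one half through regression to the mean, but the documents do not say that selection works that way. The other is that a left-right limit gives a smallest detectable change. It cancels errors shared by both sides at a visit, such as head pitch, Frankfort alignment and lip posture.

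**Conclusion.** The concern holds in a limited form. The planned individual determination has no allowance for measurement error. Under no effect, about half of subjects would appear increased on each measure (about 36% to 50% for rounding units up to one single-reading SD), and about 17% to 37% on both before any rounding (25%, or 5 of 20, if errors are independent). These figures rest on symmetric error and on an error correlation that the documents do not give. Both measures come from the profile image, so independence cannot be taken for granted.

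Individual judgements, or a count without a no-effect reference, therefore cannot support the hypothesis. The mean-change analysis is sound on this point. The weakness lies in what might be claimed about individuals and calls for a wording change, not a redesign.

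**What to change.** - **Sections 1 and 5:** delete the per-patient determination, or state that individual results are descriptive only and carry no conclusion.
- **Section 11.3:** state that the conclusion rests on the mean paired change in Goode's ratio and in the Z-angle, each with its 95% confidence interval.
- **Sections 9.1 and 11.3:** measure both quantities on the left and right profiles that Appendix A already requires, at both visits, and analyse the mean of the two sides. This reduces side-specific error only.
- Do not present a limit from left-right differences as a smallest detectable change. Its no-effect rate could be about 8% to 26% per measure for shared-error correlations of 0.3 to 0.8, against 2.5% to 3.3% with no shared error.

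The cost is protocol wording and a little more measurement on photographs already planned, with no extra visits or subjects. The sponsor gives up statements about individual responders.

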9.2 Secondary Variable Assessments

The secondary assessment is to evaluate the change in upper lip height by comparing the pre and post-injection ratio of upper lip vermilion height to lower lip vermilion height. This method was chosen because ratios eliminate any bias created by camera distance, angle, lighting, etc.

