Post OCR visits will be performed at 4 weeks following premaxillary injections. Subjects will be followed to assess any treatment-related adverse events (such as pain, nodules, swelling, redness, bruising, tenderness, itching, and headache) as well as pigmentation changes and/or keloid formation. Each subject will then be photographed with standardized photographs in a similar fashion as pre-treatment and the same measurements will be recorded.

Upon study culmination, pre-treatment and 1-month post OCR photographs will be assessed. Each patient will be evaluated to determine if nasal tip projection was increased causing an increase in upper lip projection. Additionally, the vermilion ratios will be compared to evaluate for change in upper lip vermilion height.

STUDY DURATION:

Each subject will undergo screening assessment of eligibility criteria, pre-treatment photography, and if eligible for treatment, injections of the premaxillary area. All enrolled subjects will be followed up to 1-month post OCR visit to evaluate the injections effect on nasal tip projection and upper lip projection.

OBJECTIVES:

The Primary Objective of this study is to determine the increase in nasal tip projection (measured by Goode's ratio) and the increase in upper lip projection (measured by the Z-angle) following perioral rejuvenation with premaxillary hyaluronic acid filler injections.

The Secondary Objective of this study is to assess the change in upper lip height by comparing the pre and post-treatment injection ratio of upper lip vermilion height to lower lip vermilion height.

CLINICAL HYPOTHESES:

Subjects who are treated with premaxillary injection will demonstrate an increase in nasal tip projection and have an associated increase in upper lip projection. Additionally, the upper lip will demonstrate an increase in upper lip vermilion height. As a result, the single injection site will address multiple factors that contribute to perioral aging.

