Appendix A: Photography Standardization

Appendix B: Diagram of planned measurements

Appendix A: Photo SOP**Photography and Poses**

- Use the grid feature on any of these viewers to ensure the Frankfort Plane (imaginary line from tragus to infraorbital rim) is parallel to the floor
- Stand approximately 1.5m from patient with the camera in a portrait position. The location will be marked on the floor of the photography studio.
- Ensure the patient has a relaxed expression and that their lips are closed and eyes are open for each photo.
- Give instructions like, “Slowly move you’re your chin down” or “Slowly turn your nose to the left” to achieve the desired poses listed below

Standard Poses ([contact] m)

1. Frontal
 - a. Make sure the patient doesn’t have their chin high or low by checking the Frankfort Plane. For this view, the line on the viewfinder should extend from the right tragus, across both infraorbital rims and across the left tragus. This should be parallel to the floor
2. Left Profile
 - a. For this view, ensure the patient is not rotated to the left or right (hint: look at the eyebrows to see how much of the glabella you see).
2. Right Profile
 - a. For this view, ensure the patient is not rotated to the left or right (hint: look at the eyebrows to see how much of the glabella you see).

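### The upper-to-lower vermilion ratio does not by itself show that upper lip vermilion height increased; a scaled upper height on the same photographs should support that statement

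*Combined protocol and SAP*

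**What the plan says.** The Clinical Hypotheses paragraph of the Synopsis predicts that "the upper lip will demonstrate an increase in upper lip vermilion height". The secondary objective (Synopsis and Section 3) likewise concerns change in upper lip height. Section 9.2 gives this measure for it: "evaluate the change in upper lip height by comparing the pre and post-injection ratio of upper lip vermilion height to lower lip vermilion height". Section 5 makes the intended reading explicit: "the vermilion ratios will be compared to evaluate for change in upper lip vermilion height".

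Two reasons for using ratios are given. Section 9.2 states: "This method was chosen because ratios eliminate any bias created by camera distance, angle, lighting, etc". Section 11.3 adds that, because portrait photographs vary, "the decision was made to perform measurements based on facial landmarks and distance ratios".

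On the test, Section 11.3 says only: "Statistical analysis will be conducted using a paired" *t* test. Section 5 states: "The study will enroll and treat a total of 20 subjects". There is one group and no control arm. Alpha, sidedness, effect size, standard deviation and power are not stated.

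Appendix A asks for a relaxed face and specifies that "their lips are closed and eyes are open for each photo". It also sets a head-position check and a marked camera position.

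**The concern.** The hypothesis is about one distance; the measure is a quotient of two. A higher ratio after treatment can come from a taller upper lip, a shorter visible lower lip, or both. The plan nevertheless reads any change in the quotient as a change in the numerator. The error can go the other way too: if both lips become proportionally taller, the hypothesised upper lip gain is present and the ratio misses it.

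No untreated group would show whether pose or lip seal shifted between the two sessions. The visible text does not plan to report the two heights separately, to check that the lower lip is unchanged, or to assess repeatability. At stake is whether a significant secondary result can be reported as an increase in upper lip vermilion height.

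**Working it through.** The plan gives no effect size, measurement error or power for this endpoint, so there is no figure of its own to reproduce. Only n = 20, the paired *t* test and the definition of the ratio come from the documents. Every lip dimension, error and effect below is an assumption, as is a two-sided alpha of 0.05.

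**1. What the ratio identifies.** Let R = U/L, with U the upper and L the lower vermilion height.

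- If L falls by a fraction s and U is fixed, R changes by 1/(1 − s) − 1. For s = 0.03, 0.05 and 0.10 this is +3.1%, +5.3% and +11.1%.
- From U = 7, L = 10 (R = 0.700), a 5% rise in U gives 7.35/10 = 0.735. A 4.8% fall in L gives 7/(10/1.05) = 0.735, the same value.
- A 5% rise in both gives 7.35/10.5 = 0.700, no change.

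**2. Consequence for the test.** Simulation of 20,000 trials per scenario with n = 20, and a measurement CV of 3%, 5% or 8% on each height:

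| True change | Significant rise in ratio at CV 3 / 5 / 8% |
|---|---|
| None | 2.2-2.6% throughout |
| Lower lip −5%, upper lip unchanged | 94 / 57 / 26% |
| Both lips +5% | about 2.5% throughout |
| Upper lip +5%, lower lip unchanged | 92 / 53 / 24% |

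The first row is the nominal upper-tail rate of 2.5%, so random error in L does not manufacture an increase. The last row shows that with a stable lower lip the ratio does respond to a real upper lip gain (mean change about +0.036 from about 0.70).

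**3. Precision cost of the lower lip.** On the log scale the SD of change is √(2(CVu² + CVl²)) for the ratio, and √2 × CVu for upper height if camera scale were perfectly fixed. With equal CVs the ratio's SD is √2 = 1.41 times larger. In the simulation, at CV 5%, power for a 5% upper lip gain is 0.82 for unscaled height with fixed camera scale and 0.53 for the ratio. If camera scale varies with a CV of 10%, unscaled height drops to 0.25 and the ratio stays at 0.53. Unscaled height is therefore not the remedy.

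**4. Scaling by a longer facial distance.** Take upper height u = 6-8 mm, lower height l = 9-10 mm, interpupillary distance 62 mm, the same error on each distance, and no pose error. The error cancels from the variance ratio, scaled upper height to vermilion ratio:

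(1/u² + 1/62²) / (1/u² + 1/l²)

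- 6/10 mm: 0.742, a 26% reduction.
- 8/9 mm: 0.568, a 43% reduction.
- 7/9 mm with 0.5 mm error: the ratio's CV is 0.5 × √(1/49 + 1/81) = 9.0%; the scaled upper height's is 0.5 × √(1/49 + 1/3844) = 7.2%.

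For 7/9 mm, with measurement error as the only source of variation, power for a 5% upper lip gain goes from 0.37 to 0.53 at 0.5 mm error and from 0.77 to 0.92 at 0.3 mm.

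**5. The stated rationale.** A ratio cancels a scale factor common to both distances, which deals with camera distance. It does not cancel head pitch or lighting that affects the two lips differently. The claim in Section 9.2 that all such bias is eliminated is too strong.

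**The case against.** The best defence is that the lower lip has little reason to change. Filler is placed only in the premaxillary space (Section 7, Injection Techniques). Perioral neurotoxin, ablative resurfacing and other fillers are restricted (Sections 5 and 6.2). Appendix A controls expression, lip closure, head position and camera position. A false mean increase would need a systematic fall in lower lip height after treatment, and the documents give no mechanism for one; the percentages in step 1 are illustrations. Cancelling camera scale is a real advantage of the ratio, and the objective itself names the ratio as its measure. All of this stands. It makes a stable lower lip plausible but does not verify it.

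A reader might infer that the ratio cannot show an upper lip increase at all, or that error in the lower lip measurement produces false increases. Neither is supported: with a stable lower lip the ratio tracks upper height, and random lower lip error leaves the false-positive rate at its nominal level.

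The remedy also has limits. Interpupillary distance is mainly horizontal, so it does not correct the effect of head pitch on a vertical height, and head yaw shortens it. The Appendix B measurement diagram is not visible and may already define separate heights or a reference distance.

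**Conclusion.** The point holds as a gap between the measure and the statement to be drawn from it. The ratio alone does not establish which lip changed, and the visible text provides nothing that would. Whether this would bias the result in practice is unknown, because it depends on a lower lip change that the documents neither quantify nor rule out. The gain in precision from scaling, 26-43% of measurement-error variance, rests wholly on assumed dimensions, equal error per distance and perfect pose; pose error could reduce it. The matter affects a secondary endpoint only, and the change is worth making because it is cheap and uses photographs already planned.

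**What to change.** In Section 9.2, keep the upper-to-lower ratio as the secondary measure. Add interpupillary (or inner canthal) distance, measured on the same frontal photographs; the eyes are already required to be open. Define scaled upper height and scaled lower height as each vermilion height divided by that distance. Limit the rationale to cancelling a scale factor common to both distances.

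In Section 11.3, analyse both scaled heights as supportive measures by paired *t* test with a confidence interval. State in advance that an increase in upper lip vermilion height will be reported only if the scaled upper height supports it, whatever the ratio shows. If Appendix B already defines these distances, a cross-reference to it is enough for the measurement part.

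The cost is one extra distance per frontal photograph, two additional supportive tests and a few lines of text. Residual error remains from head pitch, head yaw and the difference in depth between eyes and lips, and should be acknowledged in the report.
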